Other asthma outcomes were selected for their importance to both parents/patients and decision makers. Asthma morbidity, control, and exacerbations are of primary importance to parents, while clinicians and other decision-makers also focus on medication adherence, healthcare utilization, and exacerbations.

In addition, this study includes psychosocial outcomes of key importance to both parents and decision makers. Parents indicated a particular interest in the psychological well-being of their children, and clinicians and service providers have indicated interest in parental well-being, as this impacts a wide range of child-centered outcomes.

Analysis of the following variables is planned:

| Outcome | Measure |
|----------------------------------|--|
| Primary Outcome | |
| Symptom-free days | Days with no symptoms of asthma in prior 14d |
| Secondary Outcomes | |
| Asthma morbidity | Daytime and nighttime symptoms in prior 14d, missed school in prior 14d |
| Asthma severity | Asthma symptoms in prior 1m, and oral steroid use in prior year |
| Asthma control | Asthma symptoms in prior 1m, and oral steroid use in prior year |
| Asthma medications and adherence | Use of medications in prior 2d, and beliefs regarding asthma medications |
| Healthcare utilization | Utilization in 12m prior to enrollment and during follow-up period, including emergency department visits, hospital and ICU admissions, primary care visits, and urgent care visits. |
| Exacerbations | Courses of systemic steroids |
| Family stress | Stressful events in prior 30d |
| Parental stress | Perceived Stress Scale (PSS) |
| Parental depression | Center for Epidemiologic Studies Depression |

| | |
|------------------------------------|--|
| | Scale (CES-D) |
| Child anxiety | PROMIS Parent Proxy Anxiety |
| Child depression | PROMIS Parent Proxy Depressive Symptoms |
| Quality of life | Pediatric Asthma Caregiver Quality of Life Questionnaire (PACQLQ) |
| Caregiver smoking behavior | Cigarettes smoked per day |
| Coping strategies | Brief COPE |
| Mindfulness | Interpersonal Mindfulness in Parenting |
| Resilience | Revised Life Orientation Test (LOT-R) |
| Covariates | |
| Sociodemographics | Race, ethnicity, family history, parent education attainment, household income |
| Home exposures | Exposure to environmental tobacco smoke |
| Health literacy | Single Item Literacy Screener (SILS) |

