To address aim 2: To determine the effect that the stress management intervention has on the primary measured outcome: symptom free days. Other patient/family-centered outcomes will include parent stress, quality of life, asthma morbidity, healthcare utilization, and medication adherence. Baseline demographic characteristics will first be compared in univariate fashion between the two groups using the chi-squared test for categorical variables and the t-test for continuous variables. If any variable is not balanced by randomization, it will be used as a covariate in all secondary analyses. To test the hypothesis that the time average of number of symptom-free days over a two week period (primary outcome) at 3 and 6 month follow-up will be significantly higher among parents in Arm 2 (intervention) than in Arm 1 (usual care), a two sample t-test will be used to compare difference of mean symptom-free days over a two week period between the two arms with point estimates, 95% CI and p values being reported. Depending on the degree of dispersion, we may need to employ a Poisson or negative binomial model.

In secondary analysis, we will further explore the effect of the intervention by fitting random effect mixed models that (1) adjust for baseline covariates of interest, considered *a priori* or that differ between groups at baseline and are relevant to change in symptom-free days; (2) test for interaction between treatment effects and other covariates; and (3) examine patients who complete intervention and follow-up (per protocol analysis).

For continuous secondary outcomes, we will use the same approach as described above. For the categorical secondary outcomes, we will use the chi square test of whether relative rates between groups differ from 1. All subsequent estimates of relative rates (RR) will be adjusted (at the minimum) for age, sex, race/ethnicity and other covariates using generalized estimating equations (GEE). All estimates of RR will be reported with 95% confidence intervals (CIs). For measures of healthcare

utilization, the analysis will compare adjusted rates and RRs at 3 and 6 follow up. Depending on the degree of dispersion in the rates, these models will be based on either Poisson or negative binomial regression models.

Sensitivity analyses will be conducted to account for missing data. These will estimate the highest and lowest potential treatment effect for primary and secondary outcomes.

Missing Data

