All members of the study team will be trained in identifying adverse events and unanticipated problems. These will be reviewed by the principal investigator or co-investigator, both of whom have significant experience in patient-centered research. The IRB will be provided with reports of all adverse events and unanticipated problems, including the resulting action plan if applicable.

Any injury or harm to a study participant that is possibly related to the study intervention will be treated as an AE or SAE. Emergency department visits and hospital admissions for asthma will not be considered AEs or SAEs, as they are expected in the target population and will be tracked as outcomes. Suicide or attempted suicide will be considered an SAE. Any death, regardless of relatedness to study intervention, will be reported as an SAE.

Assuring data accuracy and protocol compliance

The study team will regularly review study processes and determine whether retraining is needed in any areas. Fidelity checklists will be utilized for both data collection and intervention protocols, and the principal investigator and co-investigator will provide ongoing supervision of staff. Data queries will be addressed in a timely manner, and retraining in data collection and data entry will be conducted as needs are identified. Any challenges identified in assuring data accuracy and protocol compliance will be reported to both the DSMB and PCORI.

I. OUTSIDE CONSULTANTS/COLLABORATORS

This project will be conducted with a number of collaborator's outside of Children's National, including:

[name]: [name] is the Director of the Johns Hopkins Adherence Research Center, and a Professor of Medicine at the Johns Hopkins University. She is a nationally recognized expert in stress and adherence, especially in asthma and in disadvantaged populations.

[name], MPH: [name] is the Medical Director at the Center for Diversity and Health Equity and Professor of Pediatrics at the University of Washington School of Medicine. [name] provides expertise in both disparities research and the use of mHealth in minority populations.

[name]: [name] is a board-certified Clinical Informaticist and Associate Professor of Emergency Medicine at the University of California Los Angeles. He provides expertise in the use of technology in clinical interventions.

J. CONTRACTUAL AGREEMENTS

None.

K. COSTS TO SUBJECTS

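### Apart from deaths and suicide or attempted suicide, harms count as AEs/SAEs only if possibly related to an intervention controls do not receive, so the SAP's AE/SAE outcome cannot be compared between arms

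*Protocol*

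**What the plan says.** Protocol section H, under the heading on identifying and reporting adverse events, gives the general rule: "Any injury or harm to a study participant that is possibly related to the study intervention will be treated as an AE or SAE". Two categories follow without that condition: "Suicide or attempted suicide will be considered an SAE", and "Any death, regardless of relatedness to study intervention, will be reported as an SAE".

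The same paragraph takes the main disease events out of the AE stream: "Emergency department visits and hospital admissions for asthma will not be considered AEs or SAEs". The reason given is "as they are expected in the target population and will be tracked as outcomes". Section D.6 accordingly lists healthcare utilization as a secondary outcome, measured "during follow-up period, including emergency department visits, hospital and ICU admissions" among other contacts. Section D.10 says of these measures that "the analysis will compare adjusted rates and RRs at 3 and 6 follow up".

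The SAP's Table of Planned Analyses has a safety row, AEs/SAEs, under Secondary Outcomes. No analysis is attached to that row. Section D.10 of the protocol has a general sentence: "For the categorical secondary outcomes, we will use the chi square test of whether relative rates between groups differ from 1". The protocol's own outcome table in D.6 does not list AEs.

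**The concern.** A secondary outcome in a randomized trial should be measured by the same rule in both arms. Here the rule refers to something only one arm receives. Two families with the same harm are treated differently: in the intervention arm it can be recorded, and in the control arm it cannot, unless it is a death, a suicide or a suicide attempt. A table of AEs by arm would then show an excess in the intervention arm if background harms are sometimes judged possibly related. It could never show a reduction in such harms, even if stress management produced one.

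The second matter is what the DSMB sees. If asthma ED visits and admissions rose in one arm, they would not appear as AEs. Whether the board would see them by arm in its regular reports depends on report content that the documents do not specify.

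**Working it through.** There is no figure in the plan to reproduce, because neither document gives an AE rate. The check is a reading of the passages side by side.

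1. **What the study intervention is.** Section D.3 identifies it as the stress management program (one-on-one sessions and peer support). Section D.2 describes the asthma clinic care as usual care, given to both arms.
2. **When controls receive it.** Section D.3 offers controls the content only once they have completed all study activities. During the period in which AEs would be counted, a control family has no exposure to it.
3. **Whether relatedness is really required.** The general sentence does not contain the word only. But the next sentences make deaths reportable regardless of relatedness. That wording is needed only if relatedness otherwise applies.
4. **Result by arm.**

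| Event | Intervention arm | Control arm |
|---|---|---|
| Death | counted | counted |
| Suicide or attempted suicide | counted | counted |
| Asthma ED visit or admission | utilization outcome, not AE | utilization outcome, not AE |
| Any other harm | counted if possibly related | cannot qualify |

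5. **Ascertainment.** Section D.5 gives controls no study contact before the follow-up interviews, apart from requests for updated contact details. Intervention parents have four sessions, support groups, texts and calls (D.3). Section H trains all staff to identify AEs, but the documents describe no harm question put to both arms. Dropping the relatedness condition alone would therefore leave unequal opportunity to detect events.
6. **DSMB.** Section H says the data compiled for the board cover safety data and study progress (enrollment, data completion and quality). It later says recommendations rest on safety, efficacy and performance data. Utilization could fall under efficacy. No sentence says that it is supplied, or that it is shown by arm.

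**Worst-case illustration only; the inputs are assumptions.** Take 207 dyads split 104 and 103, the same true proportion *r* with a harm in both arms, and a fraction *f* of intervention-arm harms judged possibly related. Expected recorded events are 104 × *r* × *f* in the intervention arm and 103 × *r* × 0 = 0 in controls. For *a* events against 0, the uncorrected chi-square is 207 × 103 × *a* / [104 × (207 − *a*)].

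| *r* | *f* | 104 × *r* × *f* | Recorded | Chi-square (p) | Fisher, two-sided p |
|---|---|---|---|---|---|
| 5% | 0.5 | 2.6 | 3 v 0 | 3.01 (0.083) | 0.25 |
| 5% | 1 | 5.2 | 5 v 0 | 5.07 (0.024) | 0.060 |
| 10% | 1 | 10.4 | 10 v 0 | 10.41 (0.0013) | 0.0016 |

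There is no true difference in any row. The rows with *f* = 1 are upper bounds for their *r*. If few harms are judged related to coaching or support groups, both arms record almost nothing and no test would be significant. The comparison would still say nothing about relative harm.

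**The case against.** Four stronger readings are tempting, and the documents do not support them.

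- **That AEs count only if related, without exception.** Deaths count in both arms, and suicide or attempted suicide has no relatedness condition. The most serious events are therefore defined alike in the two arms.
- **That asthma ED visits and admissions are lost from the safety picture.** Only the AE label is withheld. They are secondary outcomes, with rates and relative rates to be compared, and the SAP also counts hospitalizations within exacerbations. Treating expected disease events as outcomes is a reasoned choice that the protocol explains.
- **That the plan commits to a chi-square test of AEs that is loaded against the intervention.** That reading joins a general protocol sentence to a row that appears only in the SAP. Descriptive reporting fits the row equally well. The SAP does not say which is meant, and a by-arm table would carry the same asymmetry without any test.
- **That the DSMB will not see an excess of admissions.** Its remit mentions efficacy data, and it is told at once of fatal or life-threatening events. What is missing is a statement that utilization counts are shown by arm.

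It can also be said that psychological harm is watched in both arms. Elevated depression scores are reviewed within 24 hours and followed up for all participants (section F.1), and confidentiality violations are handled as unanticipated problems (section H). That is real protection for participants, but it does not make the AE/SAE outcome comparable between arms.

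**Conclusion.** The concern holds in limited form. Outside deaths and suicide or attempted suicide, the AE/SAE outcome is asymmetric by a stated rule and cannot support a comparison between arms, tested or tabulated. This rests on two readings: the study intervention is the stress management program, and the general AE sentence works as a definition. Both follow from the text. It does not depend on any event rate.

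The size of the resulting imbalance is unknown, and the p-values above should not be quoted as an expected result. The primary outcome and its analysis are unaffected. On the DSMB, the finding is a gap in specification: nothing states that asthma utilization is reported to the board by arm. This should be corrected, since a listed secondary outcome has no interpretable between-arm answer as defined.

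**What to change.** 1. **Preferred.** Ask the same closed harm question of both arms at the month 3 and month 6 interviews. Record events regardless of relatedness, and have someone other than the blinded interviewer judge relatedness as a separate item.
2. **Otherwise.** State in the SAP that AEs/SAEs are descriptive only, with no between-arm test or inference, and give the section H definition as the reason.
3. **In either case.** Add by-arm counts of asthma ED visits, hospital admissions and ICU admissions to the six-monthly DSMB report. These data are already being collected.

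The cost is one interview item at most, some SAP wording and one DSMB table. The downsides are more events to list and a small risk that an answer mentions a coach and unblinds the interviewer. A closed question keeps that risk low, and section D.6 already requires critical unblinding to be reported.

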Table of Planned Analyses

Breathe with Ease: A Unique Approach to Managing Stress (BEAMS)

PI: [name], MPH

Final 11.25.16

Primary Outcome	
Symptom-free days	
 • In last 14 days; symptom-free days are defined as a 24-hour period with no coughing, wheezing, chest tightness, or shortness of breath and no need for rescue medications
Secondary Outcomes	
Asthma morbidity	
 • In last 14d: daytime/nighttime symptoms, activity limitation, use of quick relief meds, changed plans, and missed school.
Asthma medication adherence	
 • Medication use in past 2d • Medication beliefs (difficulty following med plan, concerns re side effects, belief that med use prevents exacerbations)
Health care utilization	
 • ED visits, • hospital admissions, • ICU admissions, • primary care visits
Asthma exacerbations	
 • Courses of systemic steroids or hospitalizations in 12m prior to enrollment and during 12m follow up period (independent courses ≥ 7d apart)
Parental stress	
 • Perceived Stress Scale • Stressful Life Events
Parental depression	
 • CES-D
Child anxiety	
 • PROMIS Parent Proxy Anxiety
Child depression	
 • PROMIS Parent Proxy Depressive Symptoms
Quality of life	
 • Pediatric Asthma Caregiver Quality of Life Questionnaire (PACQLQ)
Safety data	
 • AEs/SAEs
Exploratory Outcomes	
Coping strategies	
 • Brief COPE
Mindfulness	
 • Interpersonal mindfulness of parenting
Parental Resilience	
 • LOT-R
Economic data	
 • Analysis of costs of care in both groups
Environmental smoke exposure	
 • Child smoke exposure • Parent smoking behavior
Use of existing ancillary services	
 • Use of psychological support (parent/child/other family members) • Use of mental health resources • Participation in stress reducing activities (exercise, dance, yoga, breathing, other)
Control Variables	
Baseline Sociodemographic factors	Age, gender, race, ethnicity, insurance type, parent education, household income, family medical history, parent health literacy, parental resilience
Intervention uptake, satisfaction, and fidelity	Completion of 1:1 session, completion of group sessions, location/format of sessions, use of stress management techniques, use of techniques with children
Asthma severity	
 • NAEPP classification, as determined by IMPACT DC clinician
Asthma control	
 • NAEPP classification, as determined by IMPACT DC clinician • ACT score

Table of Planned Analyses

Breathe with Ease: A Unique Approach to Managing Stress (BEAMS)

PI: [name], MPH

Final 11.25.16

We will examine interactions between primary and secondary outcomes and

- baseline asthma variables (severity/control, health care utilization, exacerbations),
- baseline psychosocial variables (parental stress and depression, resilience, child anxiety and depression, quality of life)
- baseline demographic factors

In addition, we will examine interactions between primary and secondary outcomes and intervention uptake within the intervention group.

Key planned analyses include:

- Interaction between primary outcome and parental age, education, household income, child age and gender
- Interaction between primary outcome and baseline child asthma severity, control, and history of unscheduled healthcare utilization
- Interaction between primary outcome and baseline parental depression
- Interaction between primary outcome and baseline parental stress
- Interaction between primary outcome and baseline parental resilience
- Interaction between primary outcome and baseline child depression
- Interaction between primary outcome and baseline child anxiety
- Interaction between primary outcome and baseline asthma severity/control
- Dose-response analysis of intervention uptake (session completion and parent report of technique utilization)

Sample Size Calculation: The sample size was recalculated on September 14, 2015 based on the baseline data collected from the first 60 participants, which showed the following:

- mean = 10.25 days
- standard deviation = 4.12
- median = 11.5 days.

The sample distribution is not normal and approximated a Poisson distribution. Based on this distribution, the calculated sample size is 188 to achieve 80% power at a 0.05 significance level to detect a response rate ratio of 1.15 with baseline response rate of 10.25. Therefore, with 10% percent attrition rate, we planned to enroll 207 participants.

The primary analyses for this study will be conducted at 6m FU, and the same analyses will be completed with the 12m FU data.

The primary analysis for this study will be by intention to treat.

A per-protocol analysis will also be conducted. Per protocol will be defined as completion of all four one-on-one sessions.

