The IMPACT DC Asthma Clinic is a unique program of asthma care, education and care coordination at Children’s National Health System that targets children who are heavily dependent on emergency departments for episodic care, and is designed to transition patients to more effective longitudinal asthma care in their primary medical care homes.

In its pivotal randomized controlled trial, the IMPACT DC intervention improved outcomes in multiple domains (Figures 3a and 3b).³³ Of note, it increased adjusted adherence to ICS by greater than 100% at six month follow-up [adjRR 2.03, 95% confidence intervals (1.57, 2.63)] and reduced the rate of ED visits for asthma by over 40% [adjRR 0.54, 95% confidence intervals (0.40, 0.72)]. The intervention also improved multiple other proximal and distal measures of adherence and health outcomes, including asthma-related quality of life.

| | |
|-----------|-----------|
| Figure 4a | Figure 4b |
|-----------|-----------|

While demonstrating the efficacy of IMPACT DC’s intervention within a clinical trial is impressive, IMPACT DC’s existence has also been associated with a dramatic and sustained 40% drop in the rate of ED visits for asthma among all DC youth with asthma. This drop has occurred at a time when the overall rate of ED visits for all reasons by DC youth has been steadily rising (Figures 4a and 4b).

These improvements in care and outcomes among at-risk DC youth with asthma are impressive, but significant work remains. Even within the context of IMPACT DC’s tightly scripted and guideline-based program of care, adjusted ICS adherence declined to nearly 50% within the intervention group by six months. Similarly, the rate of ED visits for asthma among DC youth in 2009 was still nearly three times the national rate.⁴ ***The guideline-based IMPACT DC intervention, like validated interventions everywhere that target asthma disparities, needs to improve further.***

C.2. Stress Management

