This study is a single blind, prospective randomized controlled trial comparing the IMPACT DC Asthma Clinic intervention of guideline-based clinical care, education, and short-term care coordination (usual care) to usual care plus parental stress management in a cohort of up to 250 parent-child dyads.

This study will employ a parallel-groups RCT design. Outcomes data will be collected by interviews at enrollment (baseline), 3 months post-enrollment, 6 months post-enrollment, and 12 months post-enrollment. The 12 month follow-up data will be collected only for a subset of participants.

D.2. Usual Care

All participants in both the usual care and intervention arms of the study will receive guideline-based asthma care in the IMPACT DC Asthma Clinic, supplemented by three months of limited care coordination services to address barriers to care.

The IMPACT DC Asthma Clinic is a fully validated and bilingual clinical intervention³³ that has operated at Children's National since 2004. It focuses on at-risk youth with an over-dependence on EDs for episodic care. It provides care to approximately 1000 new patients per year, and has won multiple national and local awards, including the EPA's 2006 National Environmental Leadership Award in Asthma Management, the 2012 DC Chartered Healthcare "*Making a Difference*" Health Disparities Award, and the 2012 DC Hospital Association *Haynes Rice Community Service Award*.

IMPACT DC's conceptual model begins with the premise that effective longitudinal asthma care is a broad continuum involving the child surrounded by his/her family, primary medical care home, hospital, ED, community pharmacist, insurance case manager, and school nurse. The vision continues with the novel idea that the ED can and should be a critical and proactive part of this continuum, particularly for children who use the ED frequently and/or are poorly connected with their medical homes. The IMPACT DC Asthma Clinic therefore targets children who are heavily dependent on EDs for episodic care. It provides a comprehensive source of asthma education, medical care, and care coordination designed to transition patients to more effective longitudinal asthma care in their primary medical care homes. Patients are referred for consultative care from EDs, inpatient units, primary clinicians, and school nurses.

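### The SAP leaves urgent care visits out of the utilization outcome that the Protocol prespecifies, so its counts alone could not separate fewer acute episodes from a change in site of care

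*SAP*

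**What the plan says.** In the Protocol (D.6 Outcomes, table of planned variables), healthcare utilization is a secondary outcome measured over the 12 months before enrollment and during follow-up, "including emergency department visits, hospital and ICU admissions, primary care visits, and urgent care visits". The same section names parent report and review of the child's medical records as the data sources. In D.10 the Protocol states how utilization is analysed: "the analysis will compare adjusted rates and RRs at 3 and 6 follow up", with Poisson or negative binomial models according to dispersion.

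The SAP (Table of Planned Analyses, marked final 11.25.16) gives the components of the same secondary outcome as "ED visits, • hospital admissions, • ICU admissions, • primary care visits". Urgent care does not appear elsewhere in the SAP, whether as a primary, secondary or exploratory outcome or as a control variable. The nearest related outcome is asthma exacerbations, defined as "Courses of systemic steroids or hospitalizations in 12m prior to enrollment and during 12m follow up period", with independent courses at least 7 days apart.

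Neither document defines a combined count of acute or unscheduled visits.

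**The concern.** A prespecified component of a secondary outcome is missing from the document that governs the analysis, and no reason is recorded. This component matters for interpretation because ED and urgent care are alternative sites for the same acute episode. The Protocol treats a lower ED rate as improvement: in C.1 it reports that the clinic's earlier randomized trial "reduced the rate of ED visits for asthma by over 40" percent. If the present trial also finds fewer ED visits in the intervention arm, readers will want to know whether the children had fewer acute episodes or were taken elsewhere. The urgent care count answers that question most directly, and the SAP does not plan to analyse it.

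**Working it through.** The documents give no sample size, power or event rate for utilization, so there is no stated figure to reproduce. The check is a comparison of definitions, followed by bookkeeping.

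**Step 1. Components side by side.**

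| Visit type | Protocol D.6 | SAP |
|---|---|---|
| ED | yes | yes |
| Hospital admission | yes | yes |
| ICU admission | yes | yes |
| Primary care | yes | yes |
| Urgent care | yes | no |

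**Step 2. What one moved visit does.** Suppose one acute episode is taken to urgent care instead of the ED.

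- Protocol list: ED −1, urgent care +1. The move is visible and the sum is unchanged.
- SAP list: ED −1, no change in any other utilization component. The record is the same as if the episode had not happened.
- SAP exacerbation outcome: the episode is counted only if systemic steroids were given or the child was admitted.
- SAP morbidity outcome: it may register as symptoms or quick-relief use, but only if it falls in the 14 days before an interview.

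**Step 3. The same in rates.** Let both arms have E acute visits per child that would go to the ED and U other urgent care visits per child. Let a fraction f of the intervention arm's ED visits move to urgent care.

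- ED rate ratio = E(1 − f)/E = 1 − f
- ED plus urgent care rate ratio = [E(1 − f) + U + Ef]/(E + U) = 1.00

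With assumed f of 0.10, 0.20 and 0.30, the ED rate ratio is 0.90, 0.80 and 0.70, and the combined ratio stays at 1.00. This is an identity, not an estimate. The documents contain no value for f.

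**Step 4. Could such a ratio reach significance?** Take the 188 participants in the sample size section as 94 per arm (1:1 is assumed), two-sided alpha 0.05 (Protocol D.10), Poisson counts and an assumed control ED rate λ per child.

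- SE of the log rate ratio = √[1/(94λ) + 1/(94λ(1 − f))]
- Chance of a significant ED reduction = Φ(|ln(1 − f)|/SE − 1.96)

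Example with λ = 1.0 and f = 0.30: SE = √(1/94 + 1/65.8) = 0.161; 0.357/0.161 = 2.22; Φ(0.26) = 0.60.

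| λ (assumed) | f = 0.10 | f = 0.20 | f = 0.30 |
|---|---|---|---|
| 0.5 | 7% | 17% | 35% |
| 1.0 | 10% | 30% | 60% |
| 1.5 | 14% | 42% | 78% |

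Overdispersion would lower these figures. They are the same under either list of components, because the ED comparison itself does not change. What differs is whether an analysed count stands beside it to show the move.

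**The case against.** The strongest reply is that the omission creates no bias in any planned estimate. The ED rate ratio falls by the same amount under the Protocol's list and the SAP's, and neither document makes ED visits the lead utilization measure. This stands. The loss is the companion count, not the validity of the ED comparison.

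It also stands that no shift by arm is documented. Clinic care and care coordination, "designed to transition patients to more effective longitudinal asthma care in their primary medical care homes" (D.2), go to both arms. Coaches are trained not to give medical advice and to refer asthma-management questions to the medical team (D.9). Support groups may include asthma-management content (D.3), so an effect on site of care is conceivable, but nothing in the intervention description concerns urgent care.

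Several stronger readings are tempting, and the documents do not support them:

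- That the SAP would score a moved visit as a benefit of treatment. This needs a differential shift that is nowhere shown.
- That the trial population is selected for heavy ED use. D.2 describes the clinic's focus in those terms, but the eligibility criteria in D.4 require no prior ED visit.
- That the exploratory cost analysis would miss the visits. The SAP does not say which costs it covers.
- That the planned moderator analysis is defective. The SAP names "baseline child asthma severity, control, and history of unscheduled healthcare utilization" without defining unscheduled utilization, so it might include urgent care.
- That primary care visits need a stated direction of benefit. The visit types are listed separately and tests are two-tailed, so opposite movements do not cancel.

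None of these replies explains why a prespecified component is absent.

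**Conclusion.** The discrepancy is exact and unexplained: the Protocol prespecifies urgent care visits within a secondary outcome and the final SAP omits them. The consequence is one of interpretation. Under the SAP's list, fewer ED visits cannot be distinguished from the same episodes treated at urgent care, except where steroids were given, the child was admitted, or the episode fell in a 14-day recall window. No size can be attached to this. The rate ratios and probabilities under the working rest on assumed shift fractions and ED rates and say nothing about how likely a shift is in this trial. The point concerns one component of one secondary outcome and leaves the symptom-free-days analysis untouched. It is worth correcting because the remedy is small and it affects what can be concluded from a utilization result.

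**What to change.** Restore urgent care visits to the SAP's health care utilization list and analyse them with the same adjusted rates and rate ratios that Protocol D.10 sets for the other components. Beside the separate components, report ED plus urgent care visits together as a supportive count of acute visits, not as a new lead measure.

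The cost is one SAP line and a little more analysis. The Protocol already plans the variable and names its sources. The limitation to state is that urgent care use outside the health system depends on parent report, so that count may be less complete than the ED count.
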